9.7 Procedure for missed and duplicated study assessments

Where, for whatever reason, assessments are not performed at their scheduled time, they shall be performed as soon as possible after identification of the omission. For repeated measurements, if the delay is more than 50% of the interval between repeated measurements, then the measurement will be regarded as missed.

With respect to capillary blood glucose concentration measurements, missed measurements will be regarded as a protocol deviation if three or more measurements are missed in one calendar day, or if the interval between any two consecutive measurements exceeds 12 hours.

The study treatment will not be stopped or suspended for missed study measurements unless the Investigator determines that this poses a specific risk to the safety of the participant. This determination will be informed by the clinical condition of the patient, and results of prior measurements.

Where study assessments have been duplicated (for example, when additional measurements have been taken as part of clinical care), the first recorded measurement after the scheduled time for that assessment will be taken as the study assessment.

9.8 Methods

All blood samples will be taken using standard peripheral venepuncture technique. Measurement of height, weight, and waist circumference will be undertaken according to published guidelines.⁷¹ The COPD Assessment Test (CAT), Exacerbations of Chronic Pulmonary Disease Tool (EXACT), and Malnutrition Universal Screening Tool (MUST) will be administered in accordance with their user instructions. Spirometric measurements will be performed in accordance with published guidelines (British Thoracic Society COPD Consortium, 2005).⁷² The McKenzie skin blanch test will be as performed as described previously.^{73,74} Blood glucose measurements will be taken using a CE-marked device licensed for this purpose.

9.8.1 Laboratory procedures

Routine blood samples for analysis in the hospital laboratory will be taken as part of standard clinical care and will be handled accordingly.

Blood samples taken for the purpose of future serum analyses will be taken directly to the study team laboratory (on-site), where samples will be centrifuged and a serum samples obtained. These will be divided into aliquots and stored at -80°C. The resulting acellular samples will be retained for future measurement of inflammatory cytokines and markers of oxidant–antioxidant balance, subject to necessary ethical and institutional approvals.

9.9 Definition of end of trial

This trial will end when the last patient attended for their follow-up appointment, or when the timeframe for this has elapsed and reasonable steps have been taken to contact the participant, to perform the follow-up assessments and to ensure the study treatment has been discontinued or, if necessary, destroyed. A few participants may not yet have received their 12-week

telephone, postal and electronic follow-up at this time. This will be undertaken as per the protocol; however, no new participants will be enrolled, and no study treatment will be prescribed, dispensed or administered, following declaration of the end of the trial.

9.10 Discontinuation/withdrawal of participants and stopping rules

9.10.1 Subject withdrawal procedure

Subject will be withdrawn from the study if they are unable or unwilling to continue the study treatment and/or follow-up arrangements.

For patients who withdraw from the study, consent will be sought to analyse the data and samples already collected. Patients withdrawn from the study will be asked to attend for follow-up as per the protocol. Patients who choose not to attend follow-up will be asked whether they can be contacted by telephone and post to establish their health status and whether any further exacerbations have occurred.

In the event that a subject is withdrawn during the study enrolment period, attempts will be made to enrol a replacement subject.

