Radiological examination requiring the administration of intravenous contrast material	Any radiological examination requiring the administration of intravenous contrast material	No earlier than 48 hours after contrast administration, if the eGFR or serum creatinine concentration is within 15% of the pre-examination value, and greater than >45 mL/minute/1.73 m ² or ≤130 µmol/L, respectively
Oral nutritional intake suspended	A 'nil by mouth' order or equivalent	Discontinuation of this order and resumption of oral intake
Substantially-reduced caloric intake	Judged by the investigator and/or clinical care team (including a dietetic specialist, where requested), on the basis of clinical history, collateral history, clinical observation, and food charts	Resumption of adequate caloric intake, as judged by the investigator, with advice from the clinical care team
Hospital readmission	A participant who, following discharge, is re-admitted to any hospital, and either (a) another stopping or suspension criterion is met, or may have been met; or (b) the investigator has concerns that the protocol cannot be safely continued (for example, if the participant is admitted to a hospital elsewhere)	When the investigator has reviewed the participant in person to ensure that no stopping/suspension criteria have been met, and that their continued participation in the trial will be safe.
Requirement for open-label glucose lowering therapy (other than insulin)	Treating clinician judges that open-label treatment with a glucose-lowering agent would be important to the participant's ongoing clinical management (unless permitted under the study protocol—that is, open-label insulin administration during the inpatient phase)	None
Withdrawal of consent:		
Participant withdraws consent	Participant reports to a member of the clinical or study team that they wish to permanently discontinue the study treatment and/or their involvement in the clinical trial	None

If a discontinuation occurs during the enrolment period, attempts will be made to recruit a substitute patient.

10 Name and description of all drugs used in the trial

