14.2 Endpoints

14.2.1 Primary endpoint

Mean capillary glucose concentration during hospitalisation period—defined as the mean of all capillary glucose measurements obtained according to the study protocol for that patient during the period between enrolment in the trial and hospital discharge. This measure has been evaluated against more complex endpoints (time-averaged glucose and hyperglycaemic index) and found to be the most practical metric of hyperglycaemia-associated risk.¹³

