14.3 Sample size and recruitment

14.3.1 Sample size calculation

In an audit and service evaluation study conducted in this centre (unpublished data, available from PI), the case notes of 20 patients hospitalised for COPD exacerbations were evaluated retrospectively. A median of 2 capillary glucose measurements were made per patient (interquartile range 1.8–3.3). The measurements had a mean value of 7.7 mmol/L and standard deviation 1.5 mmol/L. Based upon these data, a sample size of 44 (randomised equally to treatment and control groups) would allow the detection of a difference in the mean glucose concentrations between the two groups of 1.5 mmol/L with 90% power (using the *t*-distribution with a two-sided alpha of 0.05). This difference would be clinically significant and, on the basis of prior observational data,¹⁴ might correspond to a difference in the risk of adverse outcome (death or prolonged hospitalisation) of 22.5%. In the initial calculation of sample size, provision was made for an expected drop-out rate of approximately 5%, resulting in a target recruitment size of 46 patients. With effect from Substantial Amendment 4 approval, the target sample size is increased to 69 patients, with a change in the active:placebo allocation ratio from 1:1 to 2:1 (maintaining stability of the control group size). This is to permit a fuller assessment of the feasibility, safety and tolerability of the drug when used in COPD exacerbations in accordance with the accelerated dose-escalation regimen. Under conditions of 2:1 allocation, the minimum number of participants required to maintain statistical power for the primary endpoint analysis (as defined above) is 48.

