14.4.2 Primary endpoint analysis

The primary analysis will be performed in accordance with the intention to treat principle. For comparison, a per protocol analysis will be provided as a secondary outcome measure. Statistical significance shall be defined as a two-sided p-value <0.05. Any post hoc analyses will be defined as such in the research report. No interim analyses are planned.

The primary endpoint for this study will be the mean hospitalisation glucose concentration. The mean of the individual mean values recorded among participants allocated to active treatment will be compared with the mean of the individual mean values recorded among patients allocated to placebo treatment. The significance of the observed difference will be tested using an independent sample t-test.

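### Section 9.10.1 treats permanently stopping study drug as leaving the study, so glucose readings to discharge and a place in the intention-to-treat analysis are not secured

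*Protocol*

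**What the plan says.** Section 9.10.1 opens with the rule "Subject will be withdrawn from the study if they are unable or unwilling to continue the study treatment and/or follow-up arrangements". The and/or makes failure to continue treatment sufficient by itself. Three provisions follow:

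- Data in hand: "For patients who withdraw from the study, consent will be sought to analyse the data and samples already collected".
- Later contact: "Patients withdrawn from the study will be asked to attend for follow-up as per the protocol". Those who decline are asked about telephone or postal contact.
- Replacement: "In the event that a subject is withdrawn during the study enrolment period, attempts will be made to enrol a replacement subject".

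Section 9.10.2 lists the criteria for suspending or stopping treatment. Its last row puts ending the treatment and ending participation under one heading, withdrawal of consent. It closes with "If a discontinuation occurs during the enrolment period, attempts will be made to recruit a substitute patient".

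Section 14.2.1 defines the primary endpoint as the mean of each patient's protocol capillary readings "during the period between enrolment in the trial and hospital discharge", with no condition that the patient is on drug. Section 14.4.2 states: "The primary analysis will be performed in accordance with the intention to treat principle". A per-protocol analysis is offered only as a secondary comparison.

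**The concern.** An intention-to-treat estimate of a mean over the whole stay needs two things from every randomised patient: readings up to discharge, and permission to use them. Section 9.10.1 promises neither once the drug is permanently stopped. The follow-up it requests is the visit at day 28–35, or a call or letter, and none of these can supply ward glucose. Use of earlier readings is tied to a consent request, and some patients, for example those moved to critical care, may be unable to answer it.

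The patients concerned are not a random subset, because several permanent stops are triggered by worsening illness or by the glucose level. If they stop more often in one arm, or for different reasons, the comparison is biased.

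The same gap touches the purpose of Substantial Amendment 4, which enlarged the active arm to learn about feasibility, safety and tolerability. The protocol does not say that a patient who stops and is replaced stays in those denominators.

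A statistical analysis plan cannot repair this. It cannot recover readings that were not taken or may not be used.

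**Working it through.** **1. Who is affected.** Sorting the criteria in Sections 9.10.2 and 10.4:

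- *Suspension with a route back:* decompensated hypercapnic failure, severe sepsis, metabolic acidosis, renal impairment, intravenous contrast, interrupted or reduced oral intake, raised lactate with a credible other cause, hypoglycaemia due to other glucose-lowering treatment, and intolerance up to the single re-introduction attempt.
- *No route back, linked to deterioration:* critical care admission, major irreversible deterioration, severe cardiac failure, hepatic insufficiency.
- *No route back, linked to glucose:* glucose below 3.3 mmol/L not explained by other treatment; need for an open-label glucose-lowering agent other than insulin.
- *No route back, other:* allergic reaction, alcohol withdrawal, unexplained lactate of 3.0 mmol/L or more, failed re-introduction after intolerance, withdrawn consent.

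Only the last three groups fall under the withdrawal rule.

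**2. What the endpoint needs against what is secured after a permanent stop.**

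| Needed | Secured in 9.10.1 or 9.10.2? |
|---|---|
| Capillary glucose to discharge | Not mentioned |
| Use of readings already taken | Consent to be sought |
| Place in the allocated arm | Not mentioned; replacement attempted |
| Day 28–35 visit | Requested, but gives no inpatient glucose |

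**3. Is replacement needed for power?** Inputs from Section 14.3.1: difference 1.5 mmol/L, SD 1.5 mmol/L, two-sided alpha 0.05, power 90%.

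- 1:1: n per arm = 2(1.960 + 1.282)² × (1.5/1.5)² = 21.0, taken as 22, so 44 in total. This matches the protocol; noncentral-t power is 0.900.
- Drop-out: 44 × 1.05 = 46.2, against the stated 46.
- 2:1: control n = (1 + 1/2)(1.960 + 1.282)² = 15.8, taken as 16, with 32 active, so 48. This matches the stated minimum; power is 0.892.
- Target of 69 as 46 + 23: power is 0.971.
- With equal proportional loss in both arms and no replacement, power is 0.956 at 10% (41 + 21), 0.927 at 20% (37 + 18) and 0.892 at 30% (32 + 16).
- Margin already in the target: 1 − 48/69 = 30.4%.

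**4. Possible shift in the contrast.** The protocol gives no stopping rate, so these inputs are assumptions. Let a share w of an arm be lost, with a whole-stay mean D above the rest of that arm. The arm mean then moves by −w × D. With 15% lost on metformin and 5% on placebo:

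- D = 1: −(0.15 − 0.05) × 1 = −0.10 mmol/L.
- D = 2: −(0.15 − 0.05) × 2 = −0.20 mmol/L.
- Against the design difference: 0.10/1.5 = 7% and 0.20/1.5 = 13%.
- If the patients stay in but lose the second half of the stay, and only that half runs D higher, the shift is halved: −0.05 to −0.10. If the excess is constant across the stay, truncation shifts nothing.
- If those lost have low glucose (D = −1 to −2), the sign reverses: +0.10 to +0.20, against metformin.

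For scale, the standard error of the contrast at 46 v 23 is 1.5 × √(1/46 + 1/23) = 0.38 mmol/L.

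**5. Effect on type I error.** Simulation at 46 v 23, 5,000 runs, SD 1.5 within stratum, 30% of patients sicker with mean D above the others, removals only from the sicker group, no treatment effect:

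| Lost, metformin v placebo | D (mmol/L) | Two-sided type I error |
|---|---|---|
| none | 1.5 | 0.050 |
| 10% v 5% | 1.5 | 0.050 |
| 20% v 5% | 1.5 | 0.071 |
| 20% v 10% | 3 | 0.095 |
| 20% v 5% | 3 | 0.134 |

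**The case against.** The best reply is that the protocol nowhere says what it would have to say for the analysis to fail. Section 14.2.1 sets no on-treatment condition. Section 4.6.2 says glucose is monitored frequently in all inpatients. No criterion in Section 9.10.2 ends measurement. Replacement is only attempted, and no sentence removes the replaced patient from the analysis. Section 14.4.1 requires counts by arm of those assigned, treated, completing and analysed, so substitution would be visible. The consent request may cover only patients who choose to withdraw, since the next sentence speaks of those who are withdrawn.

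Most of this stands, and it rules out stronger readings that a reader might infer:

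- *That glucose is cut off and the primary result becomes an on-treatment mean, or that the 69 become 69 patients who tolerated the drug.* Both need a rule the protocol does not contain.
- *That sepsis, respiratory failure or a raised lactate generally leads to withdrawal.* The first two are suspensions with resumption criteria; lactate is permanent only without another likely cause.
- *That the bias favours metformin.* Unexplained hypoglycaemia is a permanent stop and would remove low readings. Need for another glucose-lowering agent would remove high ones, possibly more often on placebo.
- *That the audit's 14/108 (13%) needing ventilation predicts the stopping rate.* Section 11.4 says those patients had diabetes; this trial excludes treated diabetes and decompensated failure at entry.
- *That replacement harmfully duplicates the 5% drop-out allowance.* With 69 planned against 48 required, no harm follows.

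The reply does not remove the first sentence of Section 9.10.1. General inpatient monitoring is not a commitment to keep collecting trial data from someone the protocol has withdrawn from the study. A wish to analyse by intention to treat does not supply the readings or the permission.

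**Conclusion.** The point holds for permanent stops only. Section 9.10.1 makes stopping drug a form of study withdrawal and, with Section 9.10.2, attempts replacement. It does not secure the inpatient readings that Section 14.2.1 requires, or the inclusion that Section 14.4.2 promises. This is a failure to protect the analysis, not a demonstrated bias.

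Loss would be informative, but neither its size nor its direction can be fixed from the protocol. Under the assumed 10-point imbalance and 1 to 2 mmol/L excess, the shift is 0.1 to 0.2 mmol/L, which is 7 to 13% of the design difference and about a quarter to a half of a standard error. It is negligible if stops are few or balanced. The type I error becomes a real concern only with frequent, unequal loss of patients whose glucose is well above the rest. The remedy is still worth making because it is cheap and protects the primary comparison, and because replacement brings no power the trial needs.

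**What to change.** Reconcile Sections 9.10.1, 9.10.2, 14.2.1 and 14.4.2 by amendment:

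- State that stopping study drug is not withdrawal from the study.
- State that scheduled capillary glucose continues to discharge, and later assessments continue, unless the patient withdraws consent for data collection.
- State in the protocol and consent wording that data already collected are retained.
- State that every randomised patient, replaced or not, is analysed in the allocated arm for the primary endpoint and counted in the feasibility and tolerability denominators.
- Delete the two replacement sentences, or keep them with the statement above beside them.

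The cost is an amendment to the protocol and consent wording, and a few more off-treatment readings to record from a schedule that already exists. The stated sample sizes and the clinical stopping criteria do not change.

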9.10.2 Treatment suspension and stopping rules

The study treatment will be suspended or stopped under the following criteria.

Criterion	Definition	Criteria under which resumption of study treatment may be considered
Potential adverse reactions to the study treatment:		
Allergic reaction to study treatment	Any clinical reaction considered likely to represent an immune-mediated reaction to the study treatment	None
Minor side effect(s) (see also section 10.4, dose modifications)	Any side effect thought to be attributable to the study treatment, which causes distress or discomfort.	Depending on the severity of the reaction, and the wishes of the patient, this may lead to treatment suspension or dose-reduction. Subsequent resumption of treatment will be considered when the reaction has subsided
Elevated plasma lactate concentration	Plasma lactate concentration ≥ 3.0 mmol/L, with or without a co-existing abnormality that is considered likely to be the cause of the rising lactate concentration	If there was no alternative likely cause for the elevated lactate concentration, the study treatment will not be restarted. If there was a credible alternative explanation, consideration will be given to the resumption of the study treatment when the precipitant has resolved and the plasma lactate concentration is < 3.0 mmol/L
Hypoglycaemia (in association with concomitant glucose-lowering treatment)	Blood glucose < 3.3 mmol/L (near-patient capillary measurement or laboratory measurement), judged likely to be an adverse reaction to concomitant glucose-lowering therapy	Euglycaemia for at least 2 hours

Hypoglycaemia (in the absence of concomitant glucose-lowering treatment)	Blood glucose <3.3 mmol/L (near-patient capillary measurement or laboratory measurement), in the absence of, or considered unlikely to have been caused by, concomitant glucose-lowering therapy	None
Significant overall clinical deterioration:		
Admission to critical care unit	Admission of the patient to the any intensive care or high dependency unit or a plan to do so imminently	None
Major irreversible deterioration	A clinical deterioration from which the patient is deemed unlikely to survive to hospital discharge	None
Risk factors for lactic acidosis and/or hypoglycaemia:		
Decompensated hypercapnic respiratory failure	Partial pressure of carbon dioxide in arterial blood higher than the upper limit of normal, with arterial blood pH below lower limit of normal	Resolution of acidosis and no requirement for assisted ventilation for at least 48 hours.
Severe sepsis	As defined in section 7.2 (exclusion criteria)	Resolution of the episode of severe sepsis, and clinical stability for at least 48 hours, as determined by the study investigators, with input from the treating physicians as necessary
Metabolic acidosis	An arterial or venous blood pH below the lower limit of normal and an arterial or venous bicarbonate concentration (measured or calculated) below the lower limit of normal.	Resolution of the metabolic acidosis, and clinical stability for at least 48 hours, as determined by the study investigators, with input from the treating physicians as necessary (provided the criteria for discontinuation due lactate accumulation or acidosis are not met, see below)
Renal impairment	Estimated glomerular filtration rate (eGFR) <45 mL/minute/1.73 m ² or serum creatinine >130 µmol/L	Estimated GFR ≥45 mL/minute/1.73 m ² or serum creatinine ≤130 µmol/L, and it is judged that the cause of the deterioration has resolved and is unlikely to recur
Hepatic insufficiency	A clinical suspicion of liver disease in conjunction with a serum bilirubin concentration >34 µmol/L	None
Alcohol withdrawal syndrome	Clinical diagnosis of alcohol withdrawal syndrome	None
Acute coronary syndrome	Diagnosis of acute coronary syndrome by the treating physicians and/or the initiation of treatment with aspirin, clopidogrel and heparin (low molecular weight or unfractionated, at a dose recommended for the treatment of acute coronary syndrome)	The diagnosis is refuted (for example, on the basis of serial cardiac troponin measurements, or following review by a cardiology specialist)
Severe cardiac failure	Clinical diagnosis of cardiac failure by the treating physicians and/or investigator on the basis of typical symptoms and/or signs and/or results of investigations, which is leading to shortness of breath at rest	None

Radiological examination requiring the administration of intravenous contrast material	Any radiological examination requiring the administration of intravenous contrast material	No earlier than 48 hours after contrast administration, if the eGFR or serum creatinine concentration is within 15% of the pre-examination value, and greater than >45 mL/minute/1.73 m ² or ≤130 µmol/L, respectively
Oral nutritional intake suspended	A 'nil by mouth' order or equivalent	Discontinuation of this order and resumption of oral intake
Substantially-reduced caloric intake	Judged by the investigator and/or clinical care team (including a dietetic specialist, where requested), on the basis of clinical history, collateral history, clinical observation, and food charts	Resumption of adequate caloric intake, as judged by the investigator, with advice from the clinical care team
Hospital readmission	A participant who, following discharge, is re-admitted to any hospital, and either (a) another stopping or suspension criterion is met, or may have been met; or (b) the investigator has concerns that the protocol cannot be safely continued (for example, if the participant is admitted to a hospital elsewhere)	When the investigator has reviewed the participant in person to ensure that no stopping/suspension criteria have been met, and that their continued participation in the trial will be safe.
Requirement for open-label glucose lowering therapy (other than insulin)	Treating clinician judges that open-label treatment with a glucose-lowering agent would be important to the participant's ongoing clinical management (unless permitted under the study protocol—that is, open-label insulin administration during the inpatient phase)	None
Withdrawal of consent:		
Participant withdraws consent	Participant reports to a member of the clinical or study team that they wish to permanently discontinue the study treatment and/or their involvement in the clinical trial	None

If a discontinuation occurs during the enrolment period, attempts will be made to recruit a substitute patient.

10 Name and description of all drugs used in the trial

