In this study, we consider there to be a risk of lactic acidosis related to the underlying condition (COPD) and commonly associated comorbidities (such as respiratory failure, heart failure, renal failure and severe sepsis). As noted above, the lactate levels and prognosis observed in cases of lactic acidosis are believed to be dictated by with the severity of the underlying condition, rather than to the presence or plasma concentration of metformin.^{40,68} Nevertheless, given the lack of certainty over the safety of metformin therapy in such settings, and to avoid potential confusion over the aetiological agent, we shall stop or suspend the study drug if a condition develops in which there is a high risk of lactic acidosis, or if the plasma lactate concentration rises above pre-specified levels.

Further, we consider that there is a small but genuine risk of metformin-associated lactic acidosis if metformin is allowed to accumulate due to renal failure. To mitigate this, we will monitor the renal function regularly while the participant is an inpatient (when, due to the severity of their concurrent illnesses, the risk of developing renal failure is greatest), and stop or suspend the study treatment if the estimated GFR falls, or the serum creatinine rises, above pre-specified levels.

We judge that the risk of metformin-associated lactic acidosis outside the situations described above is extremely low. This risk must be balanced against the seriousness of the condition under study. As noted above, the 90-day mortality rate following hospitalisation for a COPD exacerbation is 13.9%; the 5-year mortality rate exceeds 50%. Observational data suggest that

lowering blood glucose concentration may offer the prospect of substantial benefit. As such, our assessment is that the risk–benefit balance lies in favour of undertaking this trial.

5 Study objectives

The overarching research question for this body of work is to ascertain whether metformin improves recovery from COPD exacerbations. This pilot study will address two more limited questions, as a basis for future trial design.

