7.2 Exclusion criteria

Any one of the following features

Criterion	Definition
Prior diagnosis of diabetes mellitus requiring insulin or oral hypoglycaemic therapy	Patient-reported diagnosis of diabetes, or a documented record of diabetes mellitus in the available clinical notes, requiring insulin or oral hypoglycaemic treatment
Hypersensitivity to metformin hydrochloride or to any of the excipients	Patient-reported prior reaction, or documented in available case notes
Renal impairment	Estimated glomerular filtration rate (eGFR) <45 mL/minute/1.73 m ² (using the modification of diet in renal disease (MDRD) four-variable equation), serum creatinine concentration >130 µmol/L, or a requirement for renal-replacement therapy

Severe sepsis	
Sepsis with at least one feature of organ dysfunction or tissue hypoperfusion.
 
Sepsis is defined as suspected or proven infection, plus at least two of the following features (unless they are normal for that patient at baseline):
 
 • temperature >38.3 or <36°C • white cell count <4 or >12 × 10⁹/L • acutely altered mental status • blood glucose >8.3 mmol/L 
Severe sepsis is defined as sepsis in conjunction with at least one feature of organ dysfunction or tissue hypoperfusion:
 
 • renal: creatinine >177 µmol/l or UO <0.5 ml/kg/hr for 2 hrs • hepatic: bilirubin >34 µmol/L • coagulation: platelets <100 × 10⁹/L, INR>1.5 or APTT >60 seconds • tissue hypoperfusion: any one of, systolic blood pressure systolic <90 mmHg, mean blood pressure <65 mmHg, a reduction of >40 mmHg from the patient's normal systolic blood pressure, or lactate >2 mmol/L.
Metabolic acidosis	Arterial or venous blood pH below the lower limit of normal and an arterial or venous bicarbonate concentration (measured or calculated) below the lower limit of normal
Decompensated type 2 respiratory failure	Partial pressure of carbon dioxide in arterial blood higher than the upper limit of normal, with arterial blood pH below lower limit of normal
Severe congestive cardiac failure	Clinical diagnosis of congestive cardiac failure by the treating physicians on the basis of typical symptoms and/or signs and/or results of investigations, which is felt to be the cause of shortness of breath at rest

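### Minor safety-rule error: the renal resumption criterion in Section 9.10.2 joins eGFR and creatinine with *or*, so its laboratory part can be met while the suspension criterion still holds

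*Protocol*

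**What the plan says.** The table in Protocol Section 9.10.2 opens with a mandatory rule: "The study treatment will be suspended or stopped under the following criteria". Its last column is permissive and is headed "Criteria under which resumption of study treatment may be considered".

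The renal impairment row has three parts:

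- **Suspension:** "Estimated glomerular filtration rate (eGFR) <45 mL/minute/1.73 m ² or serum creatinine >130" µmol/L. Either marker is enough.
- **Resumption, laboratory part:** "Estimated GFR ≥45 mL/minute/1.73 m ² or serum creatinine ≤130" µmol/L.
- **Resumption, judgement part**, added with *and*: "it is judged that the cause of the deterioration has resolved and is unlikely to recur".

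The intravenous contrast row of the same table sets a wait of at least 48 hours. It then asks that eGFR *or* creatinine be within 15% of its value before the examination and on the right side of the 45 and 130 limits, respectively.

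Two other sections show what the renal limits are for. Section 4.6.3 speaks of a "small but genuine risk of metformin-associated lactic acidosis if metformin is allowed to accumulate due to renal failure" and says the team will "stop or suspend the study treatment if the estimated GFR falls, or the serum creatinine rises, above pre-specified levels". Section 7.2 applies the same limits at entry, and either one excludes: an eGFR below 45, calculated "using the modification of diet in renal disease (MDRD) four-variable equation), serum creatinine concentration >130" µmol/L, or a need for renal replacement therapy.

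**The concern.** A resumption criterion should normally be the opposite of the criterion that stopped treatment, with any extra safeguards added. Here the joining word was carried over unchanged from the trigger when the inequalities were reversed, so the two criteria overlap. For a patient with one marker abnormal and one normal, the same row requires suspension and also shows the laboratory part of resumption as met. What then stands before restart is the judgement about the cause, and that clause names no laboratory level.

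At stake is the control of metformin accumulation, the one route to metformin-associated lactic acidosis that Section 4.6.3 treats as a real risk. The cell can be read as letting restart be considered with one marker still beyond its limit. The point concerns participant safety and consistent conduct across the nine listed centres. It does not touch the statistical analysis.

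**Working it through.** No figure in the plan needs to be reproduced. The check is a truth table on the wording of Section 9.10.2.

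**Inputs.** Let A = eGFR below 45 and B = creatinine above 130 µmol/L.

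- Suspension: A or B.
- Laboratory part of resumption, as written: (not A) or (not B).
- Logical opposite of the suspension rule: not (A or B) = (not A) and (not B).

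| eGFR | Creatinine | Suspend? | Laboratory part met, *or* (as written) | Laboratory part met, *and* |
|---|---|---|---|---|
| ≥45 | ≤130 | no | yes | yes |
| ≥45 | >130 | **yes** | **yes** | no |
| <45 | ≤130 | **yes** | **yes** | no |
| <45 | >130 | yes | no | no |

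**Results.**

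- Three of the four states trigger suspension. As written, 2 of these 3 also meet the laboratory part of resumption; with *and*, 0 of 3 do.
- Two states are single-marker suspensions. In 2 of 2 the laboratory part is already met at the moment of suspension, with no change in any value.
- As written, the laboratory part withholds resumption only when both markers are abnormal.

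**Can the markers disagree?** The protocol sets two limits, each able to act alone, so it allows for one being crossed without the other. As an illustration only, assume the usual MDRD form, eGFR = k × (creatinine/88.4)^−1.154 × age^−0.203 × 0.742 if female, with k = 175 or 186 and no ethnicity term. The protocol names the equation in Section 7.2 but gives no coefficients. For ages 35 to 85, eGFR then equals 45 at a creatinine of about 101–125 µmol/L in women and about 131–162 µmol/L in men. Women could have eGFR below 45 with creatinine at or below 130, and men could have the reverse. The finding does not depend on these figures.

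**Other rows of the table.**

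- *Lactate:* suspend at 3.0 mmol/L or more. Where there was a credible alternative cause, consider resuming once that cause has resolved **and** lactate is below 3.0. This is a true opposite plus a judgement, the form the renal row lacks.
- *Readmission:* resume only after review confirms that no stopping or suspension criterion is met.
- *Intravenous contrast:* each marker has a test (within 15% of its earlier value and within its limit), and the two tests are joined by *or*. The word *respectively* assigns each limit to its marker; it does not require both markers to pass. A patient with one marker stable and within its limit, and the other not, therefore passes on a literal reading.

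**The case against.** The strongest reply is that Section 9.10.2 as a whole does not authorise an unsafe restart. The opening sentence is mandatory and is not confined to a first occurrence, so a patient with either marker beyond its limit still meets the suspension criterion whatever the last column says. That column only lists when resumption may be considered, and the judgement clause must be satisfied as well. This stands as a limit on the harm. It does not remove the contradiction, because the row gives two answers for the same laboratory values and leaves the investigator to choose between them.

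A second reply is that *or* pairs each marker with its own trigger: whichever marker caused the suspension must recover. That reading is natural, but the row does not state it. It would also let the cell be met when the other marker had since become abnormal, leaving only the suspension trigger to catch it.

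A third is that monitoring would reveal a mistaken restart. Section 9.6 does require renal function at least every 72 hours to day 7 and then at least weekly, but only until discharge. It schedules no renal test between discharge and the day 28–35 visit, or at that visit. The safeguard is real for inpatients and no wider.

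A reader might also infer that the cell directly conflicts with Sections 4.6.3 and 7.2. The documents do not support that. Section 4.6.3 governs stopping and suspending, Section 7.2 governs entry, and neither sets a resumption rule. The cell is out of line with their either-marker purpose; the direct contradiction is within its own row.

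**Conclusion.** The renal resumption criterion is wrong as written, and the error is minor. Its laboratory part is not the opposite of the suspension trigger, and nothing else in the protocol says that both markers must recover before resumption. The size is 2 of 3 suspension states overlapping under *or*, against 0 of 3 under *and*.

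Two stronger inferences should be resisted. First, the protocol does not instruct sites to restart metformin in renal impairment: the suspension trigger, the judgement clause, the permissive column heading, inpatient monitoring and the separate lactate rule all remain. Second, 2 of 3 is not a patient frequency. The protocol gives no rate of discordant markers and none is claimed. Under the assumed equation, with age and sex fixed, one patient could reach only one of the two discordant states.

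The conclusion rests on reading the cell literally. Sample size, power, endpoints and analysis are unaffected.

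**What to change.** In the renal impairment row of Section 9.10.2, make the laboratory part of resumption require eGFR of at least 45 mL/minute/1.73 m² **and** creatinine of at most 130 µmol/L, and keep the judgement clause as it is.

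Make the same change in the intravenous contrast row: both eGFR **and** creatinine must be within 15% of their values before the examination and within the limits already set there. Correcting only the renal row would leave two renal rules in one table that work differently.

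The cost is a small wording change in two cells and a note to sites. The suspension triggers, thresholds, endpoints and analysis all stay the same.
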